#### **5.2.2.9. Pancreatitis**

Pancreatitis and related AEs identified by the sponsor using the list of MedDRA terms pre-specified in the charter will be sent to the independent Pancreatitis Adjudication Committee. The main analysis of events will be based on adjudicated, confirmed events in the On-Treatment analysis set. Analysis based on events occurring at any time post-randomization, regardless of the timing of the last dose of study medication, will be performed. The incidence rate and proportion of adjudicated pancreatitis events by severity will be summarized. The total number of subjects with an event not confirmed by the Pancreatitis Adjudication Committee will also be summarized.

### **5.3. Clinical Laboratory Tests**

A list of clinical laboratory assessments made during the study is provided in [Appendix 1.1](#). The percentage of subjects with specific treatment-emergent laboratory values meeting pre-defined limit of change (PDLC) criteria listed in [Appendix 1.2](#) will be summarized. The 95% CI for the percentage difference between canagliflozin compared to placebo group will be provided for each

PDLC criterion which have at least 4 or more subjects in any treatment group. A corresponding listing will also be provided. As described above, PDLC values will be presented based on measurements on study drug and up to a maximum of 2 days after the last dose of study drug, as well as all measurements regardless of the time of the last dose of double-blind study drug. Summaries based on both standard units (SI) and conventional units will be provided.

#### **5.4. Vital Signs**

A treatment-emergent vital sign abnormality is defined as a change from baseline and subsequent post-baseline value that satisfies the PDLC criteria in [Appendix 1.2](#). For each vital sign parameter, the proportion of subjects with a treatment-emergent abnormality will be tabulated by treatment group. PDLC values will be presented based on measurements up to a maximum of 2 days after the last dose of study medication.

The blood pressure measurements will be based on the average of the consecutive sitting blood pressure readings that were to be collected at each visit.

#### **5.5. Electrocardiogram**

Electrocardiogram was not be collected in this study.

## APPENDIX

### Appendix 1.1: Clinical Laboratory Tests

The clinical laboratory tests include following panels and assessments:

- Hematology panel
  - hemoglobin
  - platelet count
  - hematocrit
  - red blood cell (RBC) count
  - white blood cell (WBC) count with differential
- Serum chemistry panel
 

 
○ sodium
 
○ potassium
 
○ chloride
 
○ bicarbonate
 
○ BUN
 
○ creatinine
 
○ aspartate aminotransferase (AST)
 
○ alanine aminotransferase (ALT)
 
○ gamma-glutamyltransferase (GGT)
 
○ total bilirubin
 
	
 
○ alkaline phosphatase
 
○ creatine phosphokinase (CPK)
 
○ lactic acid dehydrogenase (LDH)
 
○ uric acid
 
○ calcium
 
○ phosphate
 
○ albumin
 
○ total protein
 
○ magnesium
 

---	---
- Fasting serum lipid profile (triglycerides, LDL-C, HDL-C, total cholesterol).
- HbA1c
- Urinalysis (dipstick analysis; from spot urine collection in the clinic on Day 1; performed at central laboratory; microscopic analysis is not required). Urine glucose will not be measured by the central laboratory
  - specific gravity - ketones
  - pH - bilirubin/urobilinogen
  - protein - nitrite
  - blood - leukocyte esterase
- Central laboratory will report the estimated glomerular filtration rate (eGFR) according to the Modification of Diet in Renal Disease Study (MDRD) equation (Levey 2006) at study visits when serum creatinine is measured. The 4-variable MDRD eGFR includes serum creatinine, age, race, and sex according to the equation below:

For creatinine in mg/dL:

$$\text{eGFR (mL/min/1.73 m}^2\text{)} = 175 \times (\text{serum creatinine})^{-1.154} \times (\text{age})^{-0.203} \times (0.742 \text{ if female}) \times (1.21 \text{ if black})$$

For creatinine in  $\mu\text{mol/L}$ :

$$\text{eGFR (mL/min/1.73m}^2\text{)} = 175 \times (\text{serum creatinine} \times 0.0113)^{-1.154} \times (\text{age})^{-0.203} \times \\ (0.742 \text{ if female}) \times (1.21 \text{ if black})$$

**Appendix 1.2: Criteria for Pre-defined Limit of Change (PDLC) and Abnormal Values**

Laboratory Test	Parameter for ANY value and LAST value
CHEMISTRY	
Albumin	Composite: <LLN and >25% decrease from BL
ALT	Absolute Value: >3X ULN
	Absolute Value: >5X ULN
	Absolute Value: >8X ULN
AST	Absolute Value: >3X ULN
	Absolute Value: >5X ULN
	Absolute Value: >8X ULN
ALT >3X ULN and Tbili >2X ULN	Composite: ALT >3X ULN and Tbili >2X ULN [with the Tbili elevation >2 X ULN within 30 days of the ALT elevation >3x ULN]
AST >3X ULN and Tbili >2X ULN	Composite: AST >3X ULN and Tbili >2X ULN [with the Tbili elevation >2 X ULN within 30 days of the AST elevation >3x ULN]
Bilirubin	Composite: >ULN and > 25% increase from BL
	Absolute Value: >2XULN
Bicarbonate	Absolute Value: <16 mEq/L
Calcium	Composite: >ULN and > 10 % increase from BL
Creatinine Kinase	Absolute Value: >1000U/L
eGFR	Composite: < 80 and decrease>30% from BL
	Change: decrease>50% from BL
Magnesium	Composite: <LLN and >25% decrease from BL
	Composite: >ULN and >25% increase from BL
Phosphorus	Composite: >ULN and >25% increase from BL
Potassium	Composite: <LLN and >15% decrease from BL
	Composite: >ULN and >15% increase from BL
	Absolute Value: $\geq 6.5$ mEq/L
Sodium	Composite: <LLN and decrease >5 mEq/L or more from BL
	Composite: >ULN and increase >5 mEq/L or more from BL
Uric Acid	Composite: <LLN and >25% decrease from BL
HEMATOLOGY	
Hemoglobin	Change: $\geq 2$ g/dl decrease from BL
	Change: $\geq 2$ g/dL increase from BL
Platelets	Composite: <LLN and decrease >25% from BL
	Composite: >ULN and increase >25% from BL
White Blood Count	Composite: < LLN and >25% decrease from BL
	Composite: > ULN and >50 % increase from BL
VITAL SIGNS	
Pulse	Absolute Value: $\leq 50$ beats per minute
	Absolute Value: $\geq 100$ beats per minute
Systolic Blood Pressure	Composite: $\geq 20$ mm Hg decrease from BL and $\leq 90$ mm Hg
	Composite: $\geq 20$ mm Hg increase from BL and $\geq 160$ mm Hg
Diastolic Blood Pressure	Composite: $\geq 15$ mm Hg decrease from BL and $\leq 50$ mm Hg
	Composite: $\geq 15$ mm Hg increase from BL and $\geq 100$ mm Hg

**Appendix 1.3: List of Preferred Terms for Selected AEs of Interest**

Diabetic ketoacidosis	Female Mycotic Genital Infections	Fracture
Acidosis	Genital candidiasis	Acetabulum fracture
Acidosis aggravated	Genital infection	Ankle fracture
Acidosis diabetic	Genital infection female	Atypical femur fracture
Acidosis metabolic	Genital infection fungal	Atypical fracture
Acidosis NOS	Urogenital infection fungal	Avulsion fracture
Acute acidosis	Vaginal infection	Bone fragmentation
Anion gap acidosis	Vaginal inflammation	Cervical vertebral fracture
Blood ketone body	Vulvitis	Chance fracture
Blood ketone body increased	Vulvovaginal candidiasis	Clavicle fracture
	Vulvovaginal mycotic infection	Closed fracture manipulation
Blood ketone body present	Vulvovaginitis	Comminuted fracture
Diabetes mellitus with ketoacidosis		Complicated fracture
Diabetes with hyperosmolarity		Compression fracture
Diabetes with ketoacidosis		Craniofacial fracture
Diabetic acidosis		Elevation skull fracture
Diabetic hyperglycemic coma		Epiphyseal fracture
Diabetic hyperosmolar coma		External fixation of fracture
Diabetic ketoacidosis		
Diabetic ketoacidotic hyperglycemic coma		Facial bones fracture
Diabetic metabolic decompensation		Femoral neck fracture
High anion gap metabolic acidosis		Femur fracture
Hyperglycemic seizure		Fibula fracture
Hyperosmolar hyperglycemic state		Foot fracture
Hyperosmolar state		Forearm fracture
Ketoacidosis		Fracture
Ketonuria		Fracture debridement
Ketosis		Fracture delayed union
Metabolic acidosis		Fracture displacement
Metabolic acidosis exacerbated		Fracture malunion
Metabolic acidosis NOS exacerbated		Fracture nonunion
Metabolic acidosis not otherwise specified (NOS)		Fracture pain
Metabolic acidosis worsened		Fracture reduction
Type I diabetes mellitus with ketoacidosis		Fracture treatment
Type II diabetes mellitus with ketoacidosis		Fractured coccyx
		Fractured ischium
		Fractured maxilla elevation
		Fractured sacrum
		Fractured skull depressed
		Fractured zygomatic arch elevation
		Greenstick fracture
		Hand fracture
		Hip fracture
		Humerus fracture
		Ilium fracture
		Impacted fracture
		Internal fixation of fracture
		Jaw fracture
		Limb crushing injury
		Limb fracture

Diabetic ketoacidosis	Female Mycotic Genital Infections	Fracture
		Loss of anatomical alignment after fracture reduction
		Lower limb fracture
		Lumbar vertebral fracture
		Multiple fractures
		Open fracture
		Open reduction of fracture
		Open reduction of spinal fracture
		Osteochondral fracture
		Osteoporotic fracture
		Patella fracture
		Pathological fracture
		Pelvic fracture
		Periprosthetic fracture
		Pubis fracture
		Radius fracture
		Rib fracture
		Sacroiliac fracture
		Scapula fracture
		Skull fracture
		Skull fractured base
		Spinal compression fracture
		Spinal fracture
		Spinal fusion fracture
		Sternal fracture
		Stress fracture
		Thoracic vertebral fracture
		Tibia fracture
		Torus fracture
		Traumatic fracture
		Ulna fracture
		Upper limb fracture
		Wrist fracture
Hepatic Injury	Hypoglycaemia	Male Mycotic Genital Infections
Acute graft versus host disease in liver	Hypoglycaemia	Balanitis
Acute hepatic failure	Hypoglycaemic coma	Balanitis candida
Acute yellow liver atrophy	Hypoglycaemic seizure	Balanoposthitis
Allergic hepatitis		Balanoposthitis infective
Ammonia increased		Erosive balanitis
Ascites		Gangrenous balanitis
Asterixis		Genital candidiasis
Autoimmune hepatitis		Genital infection
Bacterascites		Genital infection fungal
Biliary ascites		Genital infection male
Biliary cirrhosis		Penile infection
Biliary cirrhosis primary		Posthitis
Biliary fibrosis		
Bilirubin excretion disorder		
Biopsy liver abnormal		
Child-Pugh-Turcotte score increased		
Cholaemia		
Cholestasis		
Cholestatic liver injury		

Hepatic Injury	Hypoglycaemia	Male Mycotic Genital Infections
Cholestatic pruritus		
Chronic graft versus host disease in liver		
Chronic hepatic failure		
Chronic hepatitis		
Coma hepatic		
Cryptogenic cirrhosis		
Diabetic hepatopathy		
Drug-induced liver injury		
Duodenal varices		
Focal nodular hyperplasia		
Gallbladder varices		
Gastric varices		
Gastric varices haemorrhage		
Graft versus host disease in liver		
Haemangioma of liver		
Haemorrhagic ascites		
Haemorrhagic hepatic cyst		
Hepatectomy		
Hepatic adenoma		
Hepatic atrophy		
Hepatic calcification		
Hepatic cirrhosis		
Hepatic cyst		
Hepatic cyst ruptured		
Hepatic encelalopathy		
Hepatic encephalopathy prophylaxis		
Hepatic failure		
Hepatic fibrosis		
Hepatic fibrosis marker abnormal		
Hepatic haemangioma rupture		
Hepatic hydrothorax		
Hepatic infiltration eosinophilic		
Hepatic lesion		
Hepatic necrosis		
Hepatic steatosis		
Hepatitis		
Hepatitis acute		
Hepatitis cholestatic		
Hepatitis chronic active		
Hepatitis chronic persistent		
Hepatitis fulminant		
Hepatitis toxic		
Hepatobiliary disease		
Hepatocellular foamy cell syndrome		
Hepatocellular injury		
Hepatopulmonary syndrome		
Hepatorenal failure		
Hepatorenal syndrome		
Hepatotoxicity		
Hyperbilirubinaemia		
Icterus index increased		
Intestinal varices		
Ischaemic hepatitis		
Jaundice		
Jaundice cholestatic		

Hepatic Injury	Hypoglycaemia	Male Mycotic Genital Infections
Jaundice hepatocellular		
Liver and small intestine transplant		
Liver disorder		
Liver injury		
Lupoid hepatic cirrhosis		
Lupus hepatitis		
Mixed liver injury		
Nodular regenerative hyperplasia		
Non-alcoholic steatohepatitis		
Non-cirrhotic portal hypertension		
Ocular icterus		
Oedema due to hepatic disease		
Oesophageal varices haemorrhage		
Parenteral nutrition associated liver disease		
Peripancreatic varices		
Periportal oedema		
Portal hypertension		
Portal hypertensive enteropathy		
Portal hypertensive gastropathy		
Portal triaditis		
Portal vein cavernous transformation		
Portal vein dilatation		
Portopulmonary hypertension		
Radiation hepatitis		
Renal and liver transplant		
Retrograde portal vein flow		
Reye's syndrome		
Reynold's syndrome		
Splenic varices		
Splenic varices haemorrhage		
Subacute hepatic failure		
Varices oesophageal		
Varicose veins of abdominal wall		

Malignancy Bladder Cancer	Malignancy Breast Cancer	Malignancy Pheochromocytoma
Bladder adenocarcinoma recurrent	Apocrine breast carcinoma	Phaeochromocytoma
Bladder adenocarcinoma stage 0	Breast angiosarcoma	Phaeochromocytoma crisis
	Breast angiosarcoma metastatic	
Bladder adenocarcinoma stage I	Breast cancer	Phaeochromocytoma excision
Bladder adenocarcinoma stage II	Breast cancer female	Phaeochromocytoma malignant
Bladder adenocarcinoma stage III	Breast cancer in situ	
Bladder adenocarcinoma stage IV	Breast cancer male	
Bladder adenocarcinoma stage unspecified	Breast cancer metastatic	
Bladder cancer	Breast cancer recurrent	
Bladder cancer recurrent	Breast cancer stage I	
Bladder cancer stage 0, with cancer in situ		
Bladder cancer stage 0, without cancer in situ	Breast cancer stage II	
Bladder cancer stage I, with cancer in situ	Breast cancer stage III	
Bladder cancer stage I, without cancer in situ		
Bladder cancer stage II	Breast cancer stage IV	
Bladder cancer stage III	Breast neoplasm	
Bladder cancer stage IV	Breast sarcoma	
	Breast sarcoma metastatic	

Malignancy Bladder Cancer	Malignancy Breast Cancer	Malignancy Phaeochromocytoma
Bladder squamous cell carcinoma recurrent	Breast sarcoma recurrent	
Bladder squamous cell carcinoma stage 0	Contralateral breast cancer	
Bladder squamous cell carcinoma stage I	HER-2 positive breast cancer	
Bladder squamous cell carcinoma stage II	Hormone refractory breast cancer	
Bladder squamous cell carcinoma stage III	Inflammatory carcinoma of breast recurrent	
Bladder squamous cell carcinoma stage IV	Inflammatory carcinoma of breast stage III	
Bladder squamous cell carcinoma stage unspecified	Inflammatory carcinoma of breast stage IV	
Bladder transitional cell carcinoma	Inflammatory carcinoma of the breast	
Bladder transitional cell carcinoma metastatic	Intraductal papillary breast neoplasm	
Bladder transitional cell carcinoma recurrent	Intraductal proliferative breast lesion	
Bladder transitional cell carcinoma stage 0	Invasive breast carcinoma	
Bladder transitional cell carcinoma stage I	Invasive ductal breast carcinoma	
Bladder transitional cell carcinoma stage II	Invasive lobular breast carcinoma	
Bladder transitional cell carcinoma stage III	Invasive papillary breast carcinoma	
Bladder transitional cell carcinoma stage IV	Lobular breast carcinoma in situ	
Metastases to bladder	Malignant nipple neoplasm	
Metastatic carcinoma of the bladder	Malignant nipple neoplasm female	
Transitional cell carcinoma	Malignant nipple neoplasm male	
	Medullary carcinoma of breast	
	Metaplastic breast carcinoma	
	Metastases to breast	
	Mucinous breast carcinoma	
	Neuroendocrine breast tumour	
	Nipple neoplasm	
	Oestrogen receptor positive breast cancer	
	Paget's disease of nipple	
	Phyllodes tumour	
	Triple negative breast cancer	
	Tubular breast carcinoma	

Malignancy Renal Cell Cancer	Malignancy Testicular	Osmotic Diuresis
Clear cell renal cell carcinoma	Benign neoplasm of testis	Dry mouth
Clear cell sarcoma of the kidney	Leydig cell tumour of the testis	Dry throat
Denys-Drash syndrome	Sertoli cell testicular tumour	Micturition disorder
Hereditary leiomyomatosis renal cell carcinoma	Spermatocytic seminoma	Micturition urgency
Hereditary papillary renal carcinoma	Testicle adenoma	Nocturia
Metastatic renal cell carcinoma	Testicular cancer metastatic	Pollakiuria
Nephroblastoma	Testicular neoplasm	Polydipsia
Non-renal cell carcinoma of kidney	Testicular papilloma	Polyuria
Renal cancer	Testis cancer	Thirst
Renal cancer metastatic		Tongue dry
Renal cancer recurrent		Urine output increased
Renal cancer stage I		
Renal cancer stage II		
Renal cancer stage III		
Renal cancer stage IV		
Renal cell carcinoma		
Renal cell carcinoma recurrent		
Renal cell carcinoma stage I		
Renal cell carcinoma stage II		
Renal cell carcinoma stage III		
Renal cell carcinoma stage IV		
Rhabdoid tumour of the kidney		

Phimosis	Photosensitivity
Acquired phimosis	Actinic elastosis
Phimosis	Actinic prurigo
	Administration site photosensitivity reaction
	Application site photosensitivity reaction
	Chronic actinic dermatitis
	Hartnup disease
	Implant site photosensitivity
	Infusion site photosensitivity reaction
	Injection site photosensitivity reaction
	Juvenile spring eruption
	Medical device site photosensitivity
	Photodermatosis
	Photokeratitis
	Photoonycholysis
	Photosensitivity reaction
	Polymorphic light eruption
	Solar dermatitis
	Solar urticaria
	Sunburn
	Vaccination site photosensitivity

Renal Related	Severe Hypersensitivity/Cutaneous AEs	Upper UTI
Acute kidney injury	Acute generalised exanthematous pustulosis	Bacterial pyelonephritis Emphysematous pyelonephritis Kidney infection Perinephric abscess Pyelocystitis Pyelonephritis Pyelonephritis acute Pyelonephritis chronic Pyelonephritis fungal
Acute phosphate nephropathy	Allergic oedema	Pyelonephritis mycoplasmal
Acute prerenal failure	Anaphylactic reaction	Pyelonephritis viral
Anuria	Anaphylactic shock	Pyonephrosis
Azotaemia	Anaphylactic transfusion reaction	Renal abscess
Blood creatinine increased	Anaphylactoid reaction	Renal cyst infection
Blood urea increased	Anaphylactoid shock	Urosepsis
Continuous haemodiafiltration	Angioedema	
Dialysis	Circulatory collapse	
Glomerular filtration rate decreased	Circumoral oedema	
Haemodialysis	Conjunctival oedema	
Haemofiltration	Corneal exfoliation	
Hypercreatininaemia	Corneal oedema	
Neonatal anuria	Cutaneous vasculitis	
Nephritis	Dermatitis bullous	
Nephropathy toxic	Dermatitis exfoliative	
Oliguria	Dermatitis exfoliative generalised	
Peritoneal dialysis	Drug eruption	
Prerenal failure	Drug hypersensitivity	
Renal failure	Drug reaction with eosinophilia and systemic symptoms	
Renal failure acute	Epidermal necrosis	
Renal failure neonatal	Epiglottic oedema	
Renal impairment	Erythema multiforme	
Renal impairment neonatal	Exfoliative rash	
	Eye oedema	
	Eye swelling	
	Eyelid oedema	
	Face oedema	
	First use syndrome	
	Fixed drug eruption	
	Gingival oedema	
	Gingival swelling	
	Gleich's syndrome	
	Hereditary angioedema	
	Hypersensitivity vasculitis	
	Idiopathic angioedema	
	Idiopathic urticaria	
	Kounis syndrome	
	Laryngeal dyspnoea	
	Laryngeal oedema	
	Laryngospasm	
	Laryngotracheal oedema	
	Limbal swelling	
	Lip exfoliation	
	Lip oedema	
	Lip swelling	
	Mucocutaneous ulceration	
	Mucosa vesicle	
	Mucosal erosion	
	Mucosal exfoliation	
	Mucosal necrosis	
	Mucosal ulceration	
	Nikolsky's sign	

Renal Related	Severe Hypersensitivity/Cutaneous AEs	Upper UTI
	Oculomucocutaneous syndrome	
	Oculorespiratory syndrome	
	Oedema mouth	
	Oedema mucosal	
	Oral mucosal blistering	
	Oral mucosal exfoliation	
	Orbital oedema	
	Oropharyngeal blistering	
	Oropharyngeal swelling	
	Palatal oedema	
	Penile exfoliation	
	Periorbital oedema	
	Pharyngeal oedema	
	Scleral oedema	
	Shock	
	Shock symptom	
	Skin exfoliation	
	Skin necrosis	
	Small bowel angioedema	
	Stevens-Johnson syndrome	
	Stridor	
	Swelling face	
	Swollen tongue	
	Throat tightness	
	Tongue exfoliation	
	Tongue oedema	
	Toxic epidermal necrolysis	
	Type I hypersensitivity	
	Urticaria	
	Urticaria cholinergic	
	Urticaria chronic	
	Urticaria papular	
	Urticarial vasculitis	
	Vaginal exfoliation	

UTI	Venous Thromboembolic events	Volume Depletion
Bladder candidiasis	Deep vein thrombosis	Blood pressure decreased
Cystitis	Deep vein thrombosis postoperative	Blood pressure orthostatic decreased
Cystitis bacterial	Embolism venous	Dehydration
Cystitis escherichia	Iliac vein occlusion	Diastolic hypotension
Cystitis gonococcal	Inferior vena cava syndrome	Dizziness postural
Cystitis haemorrhagic	Inferior vena caval occlusion	Hypotension
Cystitis interstitial	Jugular vein occlusion	Hypovolaemia
Cystitis klebsiella	Mesenteric vein occlusion	Hypovolaemic shock
Cystitis pseudomonal	Obstructive shock	Orthostatic hypotension
Emphysematous cystitis	Portosplenomesenteric venous thrombosis	Orthostatic intolerance
Escherichia urinary tract infection	Post procedural pulmonary embolism	Postural orthostatic tachycardia syndrome
Fungal cystitis	Postpartum venous thrombosis	Presyncope
Funguria	Pulmonary embolism	Shock
Genitourinary tract infection	Pulmonary infarction	Shock symptom
Streptococcal urinary tract infection	Pulmonary microemboli	Syncope
Ureter abscess	Pulmonary oil microembolism	Urine output decreased

UTI	Venous Thromboembolic events	Volume Depletion
Ureteritis	Pulmonary thrombosis	
Uretheritis	Renal vein embolism	
Urethral abscess	Renal vein occlusion	
Urethral carbuncle	Subclavian vein thrombosis	
Urethral stricture post infection	Vascular occlusion	
Urinary bladder abscess	Venous thrombosis	
Urinary tract abscess	Venous thrombosis in pregnancy	
Urinary tract infection	Venous thrombosis limb	
Urinary tract infection bacterial	Visceral venous thrombosis	
Urinary tract infection enterococcal		
Urinary tract infection fungal		
Urinary tract infection pseudomonal		
Urinary tract infection staphylococcal		

**Appendix 1.4: Adverse Events with Potential Amputation Association**

List of selected preferred terms included within the system organ classes of infections and infestations, vascular disorders, nervous system disorders, and skin and subcutaneous tissue disorders

Infections and Infestations	Vascular Disorders	Nervous System Disorders	Skin and Subcutaneous Tissue Disorders	High Level Term (HLT) Skin and subcutaneous tissue ulcerations	
Infected skin ulcer	Arteriosclerosis	Paraesthesia	Diabetic ulcer	Penile ulceration	Medical device site erosion
Skin infection	Peripheral arterial occlusive disease	Hypoaesthesia	Neuropathic ulcer	Implant site ulcer	Ulcerated haemangioma
Staphylococcal skin infection	Peripheral vascular disorder	Diabetic neuropathy	Fungating wound	Cytomegalovirus mucocutaneous ulcer	Incision site erosion
Gangrene	Peripheral artery stenosis	Neuropathy peripheral	Diabetic foot	Skin ulcer	Incision site ulcer
Osteomyelitis	Peripheral ischaemia	Areflexia	Diabetic neuropathic ulcer	Eyelid erosion	Vaccination site ulcer
Diabetic gangrene	Arterial stenosis	Hyporeflexia	Skin erosion	Implant site erosion	Fungating wound
Localised infection	Diabetic vascular disorder	Polyneuropathy		Diabetic foot infection	Ecthyma
Wound abscess	Femoral artery occlusion	Autonomic neuropathy		Application site erosion	Perineal ulceration
Wound infection	Thrombosis	Neuropathy peripheral		Infusion site erosion	Tropical ulcer
Subcutaneous abscess	Poor peripheral circulation	Burning sensation		Mycobacterium ulcerans infection	Injection site erosion
Abscess limb	Microangiopathy	Diabetic autonomic neuropathy		Infusion site ulcer	Pyogenic sterile arthritis pyoderma gangrenosum and acne syndrome
Staphylococcal osteomyelitis	Peripheral coldness	Peripheral sensory neuropathy		Neuropathic ulcer	Scleroderma associated digital ulcer
Diabetic foot infection	Diabetic microangiopathy	Peripheral sensorimotor neuropathy		Skin ulcer haemorrhage	Vulval ulceration
Staphylococcal skin infection	Arterial occlusive disease	Sensory disturbance		Burn infection	Mucocutaneous ulceration
Soft tissue infection	Arterial thrombosis	Diabetic neuropathic ulcer		Diabetic foot	Injection site ulcer
Bone abscess	Peripheral artery thrombosis			Diabetic ulcer	Pyoderma gangrenosum
Osteitis	Arterial occlusive disease			Catheter site erosion	Scrotal ulcer
Cellulitis	Angiopathy			Pyostomatitis vegetans	Application site ulcer
Wound a	Intermittent claudication			Catheter site ulcer	Genital ulceration
Dry gangrene	Arterial disorder			Medical device site ulcer	Infected skin ulcer
Post-operative wound infection	Impaired healing a			Administration site ulcer	Diabetic neuropathic ulcer
Post-operative wound complication a				Instillation site erosion	Varicose ulceration
Wound dehiscence				Breast ulceration	Vaginal ulceration
Burn infection				Instillation site ulcer	Vulvovaginal ulceration
Extremity necrosis				Administration site erosion	Auditory meatus external erosion
				Vasculitic ulcer	Skin erosion
				Vaccination site erosion	

a Although these PTs belong in the SOC of Injury, Poisoning and Procedural Complications or in the SOC of General Disorders and Administration Site Conditions, these terms were retained for the search strategy because of their relevance

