During a routine review of unblinded interim data from the ongoing CANVAS study (DIA3008), the Independent Data Monitoring Committee observed a non-dose-dependent increase in the incidence of non-traumatic, lower-extremity amputations (mostly of the toes) in the canagliflozin 100 mg and 300 mg groups compared with placebo. With a mean duration of follow-up in CANVAS of approximately 4.5 years, the annualized incidence of lower-extremity amputation was 0.73, 0.54, and 0.30 events per 100 patient-years in the canagliflozin 100 mg, canagliflozin 300 mg, and placebo groups, respectively. Overall, treatment with canagliflozin was associated with an approximately 2-fold increase in amputation event rates (relative risk [RR] 2.15; 95% CI: 1.3- 3.5). The CANVAS/CANVAS-R IDMC, which has access to unblinded CV outcomes data, notified the sponsor that “after consideration of all outcomes, the IDMC feels the study should continue.” Infections were the events most commonly associated with amputations, and most amputations were of the toe. The factors associated with the greatest risk for amputations include prior amputation, peripheral vascular disease, and neuropathy.

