Study drug may be interrupted (eg, for safety and/or tolerability reasons such as hospitalizations for major surgical procedure or serious medical illness). Study drug interruptions, occurring for any reason and lasting 7 days or longer, will be documented on the eCRF. Study drug should be reinstated once the subject has recovered and the safety and/or tolerability concern is no longer present.

For subjects who develop conditions that are associated with or leading to amputation such as a lower extremity infection, skin ulcer, osteomyelitis, gangrene or critical limb ischemia, study drug should be interrupted until the condition has resolved in the opinion of the investigator. In the event of an amputation, restarting of dosing with canagliflozin should only be done after careful consideration of the individual risk:benefit and following discussion with the sponsor.

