#### **5.2.2.7. Amputation**

The main analysis of lower extremity amputations as documented in the dedicated case report form page will be based on the On-Study analysis set. An overview summary table with the incidence and the follow-up-adjusted incidence will be generated for:

- All lower limb amputations;
- Traumatic lower limb amputation;
- Atraumatic lower limb amputation.

Summary of anatomical region (toe, ankle, trans-metatarsal, below knee, above knee) of lower extremity atraumatic amputations will be reported by treatment group.

For atraumatic lower limb amputation, a Kaplan-Meier plot for the time to the first occurrence of event will be provided by treatment group.

For the post-treatment AEs that may be associated with amputation, groupings of selected MedDRA preferred terms used to identify events to be included in each of the following SOC categories are presented in [Appendix 1.4](#):

- Infections and Infestations;
- Vascular disorders;
- Nervous System disorders;
- Skin and subcutaneous tissue disorders;
- Osteomyelitis.

The selected preferred terms in infections and infestation are further split into “Reversible Infection” and “Irreversible Infections”. In addition, the preferred terms grouped under the MedDRA high level term of “skin and subcutaneous tissue ulcerations” are also of interest.

For each AE group listed above, the incidence of the respective preferred terms will be summarized by treatment group.

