## List of preferred terms classified as reversible infections, irreversible infections and osteomyelitis

Reversible Infections	Irreversible Infections	Osteomyelitis
Abscess limb	Diabetic gangrene	Bone abscess
Burn infection	Dry gangrene	Osteitis
Cellulitis	Extremity necrosis	Osteomyelitis
Diabetic foot infection	Gangrene	Staphylococcal osteomyelitis
Infected skin ulcer	Osteomyelitis	
Localised infection	Bone abscess	
Skin infection	Osteitis	
Soft tissue infection	Osteomyelitis	
Staphylococcal skin infection	Staphylococcal osteomyelitis	
Subcutaneous abscess		
Wound		
Wound abscess		
Wound dehiscence		
Wound infection

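### The amputation-associated adverse event summaries do not separate onset before amputation from onset after it, so part of any imbalance, mainly in the postoperative and wound terms, may be a consequence of amputation

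*SAP*

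**What the plan says.** SAP 5.2.2.7 has two parts. The main amputation analysis uses the dedicated case report form page and the On-Study set. A second, descriptive part takes adverse events that may be linked to amputation, identified by the preferred terms of Appendix 1.4. Its output is specified as follows: "For each AE group listed above, the incidence of the respective preferred terms will be summarized by treatment group". The section gives no rule on onset relative to the amputation date, no restriction to subjects with or without an amputation, and no exclusion of events that follow a procedure.

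In Appendix 1.4 the Infections and Infestations column holds "Diabetic foot infection", gangrene and osteomyelitis together with "Post-operative wound infection", "Post-operative wound complication" and Wound dehiscence. Impaired healing sits under Vascular Disorders. Footnote a says of Wound, Post-operative wound complication and Impaired healing that "these terms were retained for the search strategy because of their relevance". It explains why terms from other system organ classes were kept.

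The further split in Appendix 1.4 places Wound, Wound infection and "Wound dehiscence" among the reversible infections. The two Post-operative terms do not appear in that split.

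**The concern.** Infection, ulcer, ischaemia or gangrene before an amputation may be part of the path to it. A wound infection or dehiscence afterwards may be a result of it. The planned table counts both in the same way. If one arm has more amputations, it has more subjects in whom such later events can occur, even when the precursor conditions are equally frequent in both arms.

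This bears on a live safety question. Protocol 1.1.2 reports that in interim CANVAS data "the annualized incidence of lower-extremity amputation was 0.73, 0.54, and 0.30 events per 100 patient-years" for canagliflozin 100 mg, canagliflozin 300 mg and placebo, with an overall relative risk of 2.15 (95% CI 1.3 to 3.5). It adds that infections were the events most often associated with amputation. Readers will therefore look at this table to judge whether canagliflozin raises infection or ischaemia ahead of amputation. Without dates, the table cannot separate that from the aftermath of amputation.

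**Working it through.** **Passages side by side.** Protocol 6.1 gives its own examples of precursor conditions: "For subjects who develop conditions that are associated with or leading to amputation such as a lower extremity infection, skin ulcer, osteomyelitis, gangrene", and then critical limb ischaemia. It names no postoperative term. Appendix 1.4 covers these conditions and adds four terms that can follow surgery. Reporting by preferred term lets a reader set aside the two Post-operative rows. It does not help with Wound infection, Wound dehiscence, Cellulitis, Osteomyelitis or Gangrene, where one row can hold events from before and after an amputation.

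The plan states no figure for this table, so there is none to reproduce. What follows is an illustration of size.

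**Inputs from the documents.**
- Subjects: 5,812 randomised 1:1 (SAP 1.1), so n = 2,906 per arm.
- Placebo amputation rate 0.30 per 100 patient-years and relative risk 2.15 (Protocol 1.1.2). Check: (0.73 + 0.54)/2 = 0.635, and 0.635/0.30 = 2.12, in line with 2.15.

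**Assumptions not in the documents.**
- CANVAS rates carry over to CANVAS-R, and events per patient-year are treated as subjects with an amputation.
- Mean follow-up is 1.5 to 3 years.
- A share f = 5% to 30% of amputees have a collected postoperative wound event.
- A share o = 0 to 90% of those subjects already count through an earlier listed event.
- The background share of subjects with any listed event is b = 2% to 10%, equal in both arms.

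**Expected amputees, placebo versus canagliflozin** (n × years × 0.0030, then × 2.15):
- 1.5 years: 13.1 versus 28.1
- 2 years: 17.4 versus 37.5
- 3 years: 26.2 versus 56.2

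**Whole list.** Ratio = [n·b + A_c·f·(1 − o)] / [n·b + A_p·f·(1 − o)], where A_c and A_p are the amputees on canagliflozin and placebo.
- Smallest at o = 0 (1.5 years, f = 5%, b = 10%): (290.6 + 1.41)/(290.6 + 0.65) = 1.003.
- Largest at o = 0 (3 years, f = 30%, b = 2%): (58.12 + 16.87)/(58.12 + 7.85) = 1.14.
- The same largest case at o = 90%: (58.12 + 1.69)/(58.12 + 0.78) = 1.015.
- Extra canagliflozin subjects, (A_c − A_p)·f·(1 − o): from 15.0 × 0.05 = 0.75 to 30.1 × 0.30 = 9.0 at o = 0, and one tenth of that at o = 90%.

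**Postoperative terms alone, 2 years.** Let b0 be the share of subjects with such an event after other surgery.
- b0 = 0: the ratio equals the amputation relative risk, 2.15.
- b0 = 0.1%, f = 30%: (2.91 + 11.25)/(2.91 + 5.23) = 1.74.
- b0 = 0.5%, f = 5%: (14.53 + 1.87)/(14.53 + 0.87) = 1.07.

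**Sensitivity to the relative risk.** In the largest whole-list case, the interval limits 1.3 and 3.5 give (58.12 + 10.20)/65.97 = 1.04 and (58.12 + 27.46)/65.97 = 1.30. With equal amputation rates the ratio is 1.

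**The case against.** The case against is substantial, and most of it limits the size of the point.

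- The four terms are generic. They cover any operation or wound, and Wound dehiscence and Impaired healing can also come before an amputation.
- The SAP claims only a possible association with amputation. A broad descriptive search may legitimately include sequelae.
- The SAP plans incidence by preferred term. It plans no pooled rate ratio, hazard ratio or test on this list.
- Incidence counts subjects (SAP 5.2.2), so an amputee with an earlier listed ulcer or infection adds nothing to a group total.
- SAP 5.2.1 limits collection to serious events, events leading to discontinuation and selected events of interest, so many minor wound events will not be recorded.
- The relative risk of 2.15 is from interim CANVAS data. It is not a CANVAS-R result.

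A larger distortion can be calculated. With precursors at 0.1 per 100 subject-years and 10% to 40% of amputations followed by a complication, (0.1 + 0.635f)/(0.1 + 0.30f) runs from 1.26 to 1.61. A reader might take that as the likely size. It is not a sound guide, because it makes all the listed conditions rarer than amputation itself and counts every complication as a new subject. With precursors at 1.0 per 100 subject-years the same formula gives 1.03 to 1.12.

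Two things remain. The infection, wound and gangrene rows stay ambiguous without dates. Restricted collection also does not remove the problem, because an event that causes or prolongs hospitalisation is serious under Protocol 12.1.1 and is collected.

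**Conclusion.** The gap is real and modest. SAP 5.2.2.7 does not order the Appendix 1.4 events against the amputation date, so the table cannot separate precursors from sequelae. For the list as a whole, a ratio of about 1.00 to 1.14 could arise with equal precursors. That rests on the assumed follow-up, complication share, overlap and background incidence, and on the interim relative risk of 2.15; at the upper confidence limit of 3.5 the most extreme case reaches 1.30. The effect is concentrated in the postoperative terms: 1.07 to 1.74 with some background surgery, and 2.15 if every such event follows an amputation.

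A reader might infer that the arm with more amputations must show more associated events by construction, or that the list counts complications of amputation surgery as such. The documents do not support either. No term is tied to amputation surgery, the terms at issue are few, and footnote a concerns system organ class membership. Nothing here touches the main amputation analysis or any hypothesis test.

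**What to change.** Keep the planned all-events table in SAP 5.2.2.7. Add a supplementary split of each Appendix 1.4 summary by onset before, on the same day as, or after the subject's first lower-limb amputation. Events in subjects without an amputation count as before. Same-day onsets need their own column because a precursor may be recorded on the date of surgery. If rates are shown, truncate at-risk time at the amputation. Show the postoperative and wound-healing terms on their own lines. Name the analysis set as well: the section names none for these events, which it calls post-treatment, while SAP Section 5 defaults to On-Treatment.

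The cost is SAP wording, one date comparison per event and one more descriptive table with small counts. No new data should be needed, since the planned Kaplan-Meier plot of first atraumatic lower-limb amputation already requires that date.

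The pre-amputation part should not replace the main table. It truncates at a post-randomisation event that treatment may affect. It also drops infections or gangrene preceding a second amputation, although Protocol 1.1.2 names prior amputation among the strongest risk factors. It should be read as descriptive only.
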